3.1 Characteristics

We will prospectively enroll four hundred HIV-positive women to undergo cervical cancer screening at FACES-supported MOH clinics in Kisumu County. After informed consent, clinical and demographic information will be collected, and participants will undergo cervical cancer screening using HPV testing. Women who previously screened positive for HPV (within the last 3 months) but have not undergone treatment will also be eligible for recruitment. Women with a positive HPV test will be evaluated for treatment with thermal coagulation, per WHO standards of ablative treatment. Per the WHO and Kenya Ministry of Health guidelines, women who will be candidates for thermal coagulation if the squamocolumnar junction is fully visualized, the cervical lesion covers less than 75% of the cervix, and there is no endocervical component or suspicion of cancer.⁸ Women who are not candidates for ablation will be referred to nearby a referral facility. All participants with a positive HPV test will undergo directed biopsy just prior to treatment for disease ascertainment but proceed to have same-day treatment, according to the WHO guidelines for screen & treat.

At 12-months after treatment, all participants treated at baseline will undergo repeat colposcopy, directed biopsy for those with cervical abnormalities or those with CIN2/3 at baseline, as well as provider collected HPV testing for persistence. Twenty-five percent of women with normal colposcopy will have a random biopsy at 6 or 12-O'Clock to confirm the absence of disease. Pain will be assessed immediately following treatment using a visual analog scale (VAS). The presence and severity of AEs will be assessed 4-6 weeks following treatment via a phone call, or in person visit, if warranted. Healthcare providers offering thermal ablation for the treatment of precancerous lesions will be surveyed at 4-6 week follow-up to evaluate provider acceptability and satisfaction with this treatment method.

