5.7.2 Provider Acceptability Evaluation

At 4-6 week follow up, providers will be surveyed using a Provider Acceptability survey, modified from the System Usability Scale to evaluate provider acceptability and satisfaction with the use of thermal coagulation for treatment of precancerous lesions.³²

5.8 12 Month Follow-up Exam

At approximately 12-months after treatment, all participants treated at baseline will undergo repeat colposcopy, biopsy for those with CIN2/3 at baseline or those with suspicious lesions on colposcopy, as well as provider collected HPV-collection for persistence. Twenty-five percent of women with normal colposcopy will have a random biopsy at 6 or 12-O'Clock for ascertainment and avoidance of verification bias.

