7.1 Primary Objective

To evaluate the efficacy of thermal coagulation for the treatment of HIV-positive, HPV-positive women by assessing rates of HPV persistence and CIN2/3 at 12 months after treatment

Four hundred HIV-positive women with positive HPV testing will undergo colposcopy-directed biopsy for disease ascertainment prior to same-day treatment with thermal coagulation. At 12-months after treatment, all participants will undergo repeat HPV testing for persistence, and those who are HPV-positive will undergo repeat colposcopy, and biopsy as indicated for abnormal results, or random biopsy for 25% of those with normal colposcopy. We will define cure as a normal biopsy result or normal colposcopy among those who do not receive a biopsy.

Statistical Analysis: We will report the proportion of women with no evidence of cervical dysplasia at 12-months (primary outcome) follow-up, including 95% confidence intervals. We will extrapolate the rate of disease among those with normal colposcopy based on the rate of disease among the 25% in this group who will receive biopsy, and this will be incorporated in calculating persistence. We will perform a logistic regression to examine predictors of treatment success, using clinical and demographic variables as predictor variables. We will also report the rate of persistence of HPV at follow-up and compare with rates reported in the literature in this same population. We will compare efficacy rates for clearance of CIN2/3 to historical results following cryotherapy treatment in similar settings. A one-sample exact test will be used to compare the obtained efficacy proportion to that of historical controls.

We will leverage the robust infrastructure of the FACES in which patients are seen every one-to three months, and there is an established patient tracing system (including home visits) to reduce loss-to-follow-up. With a loss-to-follow-up rate of 10%, we will still be powered to answer this objective. Prior studies at this clinic have been able to achieve > 90% follow-up rate.³⁶ While limited by the lack of randomization to cryotherapy versus thermocoagulation, this study will provide pilot results that may enable a future randomized study evaluation of these two treatment methods.

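### The planned regression of treatment success carries no correction for a 12-month biopsy schedule that depends on baseline CIN2/3, so if it includes all treated women, predictors of baseline disease can look like predictors of failure

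*Combined protocol and SAP*

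**What the plan says.** Sections 3.1 and 5.8 agree on the 12-month assessment. All treated women have colposcopy. Section 3.1 then calls for "directed biopsy for those with cervical abnormalities or those with CIN2/3 at baseline", and 5.8 for "biopsy for those with CIN2/3 at baseline or those with suspicious lesions on colposcopy". For the rest, 3.1 says: "Twenty-five percent of women with normal colposcopy will have a random biopsy at 6 or 12-O'Clock to confirm the absence of disease". Section 5.8 repeats the 25% and gives avoidance of verification bias as the reason.

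Section 7.1 supplies the only definition of success: "We will define cure as a normal biopsy result or normal colposcopy among those who do not receive a biopsy". It extrapolates disease from the biopsied quarter to the other women with normal colposcopy, and says that "this will be incorporated in calculating persistence". It then states: "We will perform a logistic regression to examine predictors of treatment success, using clinical and demographic variables as predictor variables". No population, outcome coding, weighting or adjustment for who was biopsied is given for that model. Section 5.9 lists the candidate variables, among them age, CD4 count and antiretroviral use. Baseline histology is not on the list.

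Section 7.1 also gives its own 12-month schedule. All women have an HPV test, and "those who are HPV-positive will undergo repeat colposcopy, and biopsy as indicated for abnormal results", with a random biopsy for 25% of those with normal colposcopy. It does not call for biopsy because of baseline CIN2/3.

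**The concern.** Under 3.1 and 5.8, how hard one looks for residual disease depends on baseline histology. With a normal 12-month colposcopy, a woman who had CIN2/3 is always biopsied, while a woman who did not has a 25% chance. Hidden disease in the other 75% is recorded as cure. Extrapolation can repair an aggregate rate, but it does not change the woman-level outcome that enters a logistic model. Because baseline grade is not a listed covariate, nothing in the model would absorb the difference.

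A variable that predicts only who had CIN2/3 at baseline could therefore be reported as a predictor of failed thermocoagulation in HIV-positive women.

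**Working it through.** **Plan's figures.** Section 3.3 expects 35% of 400 women to have CIN2/3: 0.35 × 400 = 140, leaving 260 without. After 14% loss, 140 × 0.86 = 120.4, against the stated 120. Both reproduce.

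**Inputs from the plan.** The probability of biopsy after normal colposcopy (v) is 1.00 with baseline CIN2/3 and 0.25 without (3.1, 5.8). True failure F = 1 − 0.772 = 22.8%, from the historical cryotherapy efficacy in 3.3.

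**Assumptions not in the documents.** F is the same in both groups (the null case). The share s of residual disease visible at colposcopy runs from 1.0 to 0.5. A binary predictor X acts only on baseline CIN2/3, with 50% CIN2/3 when X is present and 20% when absent (average 35%). A biopsy finds the disease that is there.

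**Formula.** Observed failure = F·s + F·(1 − s)·v. With baseline CIN2/3 this is always 22.8%. Without it, at s = 0.5, it is 0.228 × (0.5 + 0.5 × 0.25) = 0.1425. The odds ratio for baseline CIN2/3 is (0.228/0.772) ÷ (0.1425/0.8575) = 1.78. For X, observed failure is 0.5 × 0.228 + 0.5 × 0.1425 = 0.185 when present and 0.2 × 0.228 + 0.8 × 0.1425 = 0.160 when absent, an odds ratio of 1.20.

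| Visible share s | Observed failure, with CIN2/3 | Observed failure, without | Spurious OR, baseline CIN2/3 | Spurious OR, X |
|---|---|---|---|---|
| 1.0 | 22.8% | 22.8% | 1.00 | 1.00 |
| 0.9 | 22.8% | 21.1% | 1.11 | 1.03 |
| 0.8 | 22.8% | 19.4% | 1.23 | 1.06 |
| 0.7 | 22.8% | 17.7% | 1.38 | 1.10 |
| 0.5 | 22.8% | 14.3% | 1.78 | 1.20 |

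**Simulation** (400 women, 2,000 replicates). The results agree with the table. The false-positive rate for X at a nominal 5% is about 5–6% for s of 0.7 or more, and 9.4% at s = 0.5.

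**If a blind biopsy finds only half of hidden disease.** At s = 0.5, observed failure is 0.228 × (0.5 + 0.5 × 0.5) = 17.1% with CIN2/3 and 0.228 × (0.5 + 0.5 × 0.25 × 0.5) = 12.8% without. The odds ratios fall to 1.40 and, for X, 1.11.

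**If failure truly differs** (22.8% with and an assumed 8% without baseline CIN2/3). X then has a real odds ratio of about 1.47. The schedule inflates it to about 1.55 at s = 0.8 and 1.72 at s = 0.5.

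**Under the biopsy rule in 7.1** (no baseline-CIN2/3 trigger; its restriction of colposcopy to HPV-positive women was not modelled). The null odds ratio for X is 0.99–1.01.

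**Remedies, null case, 3.1/5.8 schedule.** Weighting the randomly biopsied women without baseline CIN2/3 by 1/0.25 gives a median odds ratio for X of 0.99–1.01 at every s. Restricting the model to baseline CIN2/3 gives 0.97–0.99.

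**The case against.** The strongest objection is that the problem comes from joining the biopsy rule of 5.8 to the cure definition of 7.1, when 7.1 has its own schedule without the baseline-CIN2/3 trigger. This stands as a limit on the point. Under 7.1 the stated mechanism disappears, but the plan is not rescued. Verification would then depend on 12-month HPV status, and an HPV-negative woman without colposcopy fits neither part of the cure definition.

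Second, the regression population is not stated. The hypothesis in 2.1 and the sample size in 3.3 concern CIN2/3, and a model limited to those women is free of this bias. That also stands. The other reading is at least as natural: 7.1 opens with all 400 women, and under 5.8 the clause on women not biopsied would apply only to women without baseline CIN2/3.

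Third, the reach is limited. Predictors of success are not an objective or endpoint in section 2, 7.1 describes the results as pilot, and the effect on listed variables is modest. This is correct and sets the weight of the point.

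A reader might infer from 100% against 25% that spurious associations are certain and about fourfold. The documents do not support that. A fourfold contrast in recorded failure needs colposcopy to show no residual disease at all and hidden disease to be equally common in both groups; the documents give no figure for either. A reader might also infer that the primary proportion is biased in the same way. Section 7.1 plans an extrapolation for that quantity, and under 3.1/5.8 the CIN2/3 group is uniformly biopsied.

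**Conclusion.** The point holds conditionally. Under the 3.1/5.8 schedule and the 7.1 cure definition, a regression in all treated women has an outcome verified differently by baseline histology, and no planned correction reaches it. If colposcopy misses some residual disease, predictors of baseline CIN2/3 can look like predictors of failure.

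With equal true failure of 22.8% and 90% down to 50% of disease visible, the spurious odds ratio is about 1.1–1.8 for baseline CIN2/3 and about 1.03–1.20 for a variable linked only through it, with false-positive rates of about 5–9%. The visible share, the 50%/20% split and equal failure are assumptions; the biopsy fractions are the plan's. There is no bias if colposcopy misses nothing or the model is limited to baseline CIN2/3. Part of any association seen may be real. The point merits correction in the analysis plan but does not threaten the main comparison.

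**What to change.** First reconcile the 12-month schedules in 3.1 and 5.8 with the one in 7.1; the remedy depends on which applies. Then, given the 3.1/5.8 schedule, amend 7.1 as follows:

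- Fit the logistic regression in women with baseline CIN2/3, with the 12-month biopsy result as outcome. Treat a missing biopsy as a missing outcome, not as cure.
- If a model in all treated women is also wanted, do not enter unbiopsied women as cured. Use women with 12-month histology, and weight the sampled women without baseline CIN2/3 and with normal colposcopy by the inverse of the realised sampling fraction (planned 1/0.25 = 4). Give the others weight 1, use robust standard errors and include baseline grade.
- State that the 25% are chosen by chance. As written, random describes the biopsy, not the selection of the woman.

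This needs only analysis-plan wording, with no extra biopsies. The cost is precision. The restricted model has about 140 women, or 120 after loss; at 22.8% failure that is about 32 (140 × 0.228) or 27 (120 × 0.228) failures, so few of the variables in 5.9 can be fitted together. The weighted model leaves out the unbiopsied women.

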5.4 Baseline Colposcopy and Cervical Biopsy

All women with a positive HPV screening test will undergo a colposcopy exam followed by a directed biopsy of abnormal areas using a punch biopsy forceps. If there are no abnormal areas, a random biopsy will be performed at 6 or 12 O'clock. Colposcopy exam will be done in accordance with the International Federation for Cervical Pathology and Colposcopy (IFCPC) guidelines, including sequential evaluation using a green filter and acetic acid.²⁷ During the cervical biopsy, the study clinician will use a biopsy forceps to obtain a rice-grain-sized cervical specimen, either at the site of abnormality or at random quadrants. The specimen(s) will be placed in a container with formalin, labeled and stored while awaiting transportation to pathology.

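### The 12-month biopsy required of women with baseline CIN2/3 has no stated site when colposcopy is normal, and nothing ties it to the baseline lesion, so missed residual disease would count as cure

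*Combined protocol and SAP*

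**What the plan says.** **Who is biopsied at 12 months.** Section 3.1 plans "directed biopsy for those with cervical abnormalities or those with CIN2/3 at baseline". Section 5.8 plans "biopsy for those with CIN2/3 at baseline or those with suspicious lesions on colposcopy". In both, baseline CIN2/3 is enough to require a biopsy, whatever colposcopy shows. Section 7.1 differs: "those who are HPV-positive will undergo repeat colposcopy, and biopsy as indicated for abnormal results, or random biopsy for 25" per cent of those with a normal colposcopy. There, baseline CIN2/3 is not a trigger, and colposcopy depends on HPV status.

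**Where the biopsy is taken.** At baseline, section 5.4 directs the biopsy to abnormal areas and adds: "If there are no abnormal areas, a random biopsy will be performed at 6 or 12 O'clock". The same section describes the specimen as coming from "either at the site of abnormality or at random quadrants". At 12 months the only stated site belongs to a different group: "Twenty-five percent of women with normal colposcopy will have a random biopsy at 6 or 12-O'Clock" (5.8, with the same rule in 3.1). No site is given for a woman with baseline CIN2/3 and a normal colposcopy.

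**What is recorded.** Section 5.4 has specimens labelled but does not ask for a clock position. The data items in section 5.9 include no lesion site.

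**How the result is scored.** Section 7.1: "We will define cure as a normal biopsy result or normal colposcopy among those who do not receive a biopsy". HPV persistence is a separate endpoint (2.2) and does not override a normal biopsy.

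**The concern.** Women with baseline CIN2/3 carry the non-inferiority comparison in section 3.3, and their 12-month biopsy is meant to prove cure histologically. Section 3.1 calls that biopsy directed, but a normal cervix shows nothing to direct it to. A clinician who looks for guidance finds only the 6 or 12 o'clock rule, which has no link to where the disease was. A woman whose CIN2/3 lay at 3 o'clock could then be sampled at 6 o'clock, have a normal result and be scored as cured.

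This error can only turn an uncured woman into a cured one. It therefore raises the apparent cure rate and favours a non-inferiority finding. The extrapolation planned in 7.1 does not correct it, because it uses random biopsies at the same clock positions and cannot recover disease that those positions miss. The study's stated contribution is biopsy-verified efficacy (1.4, 1.5), and 3.5.1 justifies the random biopsies as a guard against verification bias, so the gap works against the plan's own aim.

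**Working it through.** **Inputs from section 3.3.** Expected women with CIN2/3: 400 × 0.35 = 140. Boundary: 77.2% − 10 points = 67.2%. One-sided alpha is 0.025. After 14% loss, 140 × 0.86 = 120.4, so n=120. Section 7.1 names a one-sample exact test.

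**The plan's own figure.** Section 3.3 states 90% power at n=140 with a difference of 0.0102, that is, a true rate of 78.22%. A normal approximation using the variance at the alternative gives 88.5%; the exact test gives 79.6%. The figure is context only, and this point does not depend on it.

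**Decision rule.** With n=140, the smallest cure count whose upper-tail probability at 67.2% is at most 0.025 is 106 (106/140 = 75.7%). P(X ≥ 106 | 140, 0.672) = 1.8%. With n=120 the count is 92 (76.7%) and the probability is 1.5%.

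**Misclassification (assumed).** Let f be the share of residual disease that is invisible at colposcopy and h the chance that an untargeted biopsy hits it. The share of uncured women scored as cured is q = f × (1 − h). The documents give neither f nor h. With f from 0.1 to 0.4 and h from 0.25 to 0.75, q runs from 0.1 × 0.25 = 0.025 to 0.4 × 0.75 = 0.30.

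**Case A: historical rate free of this error.** True cure is at the boundary, so apparent cure = 0.672 + 0.328 × q.

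**Case B: historical cohort with the same q.** The reported 77.2% is then itself inflated, and its true rate is t = (0.772 − q)/(1 − q). A new treatment truly 10 points worse has true cure t − 0.10. Its apparent cure is (t − 0.10) + (1.10 − t) × q, which simplifies to 0.772 − 0.10 × (1 − q).

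The decision count is unchanged in both cases.

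| q | A: apparent cure | A: false NI, n=140 | A: false NI, n=120 | B: apparent cure | B: false NI, n=140 |
|---|---|---|---|---|---|
| 0 | 67.2% | 1.8% | 1.5% | 67.2% | 1.8% |
| 0.025 | 68.0% | 2.9% | 2.4% | 67.5% | 2.1% |
| 0.10 | 70.5% | 10.1% | 8.1% | 68.2% | 3.2% |
| 0.30 | 77.0% | 68.7% | 58.9% | 70.2% | 8.9% |

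In case A the apparent cure rate rises by 0.328 × 0.025 = 0.8 points to 0.328 × 0.30 = 9.8 points. In case B it rises by 0.10 × 0.025 = 0.25 points to 0.10 × 0.30 = 3.0 points. Both cases move toward apparent efficacy; the size depends on q and on how the historical cohort was assessed.

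**The case against.** **The 6 or 12 o'clock rule is not written for these women.** A reader might infer that the plan sends women with baseline CIN2/3 and a normal colposcopy to 6 or 12 o'clock. It does not. Sections 3.1 and 5.8 put them in one clause and the 25% random sample in another, and a directed biopsy in a woman with a known lesion could be read as aimed at the treated area. This stands: the site is unspecified, and 6 or 12 o'clock is only the nearest default. But 5.4 uses directed for visible abnormal areas and sends a cervix without any to a random site, so the favourable reading is not secured.

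**Not all residual disease elsewhere would be called cure.** Visible lesions are biopsied. The error needs disease that is both invisible and missed, and where the baseline CIN2/3 was itself found at 6 or 12 o'clock the sites may coincide. This stands. The plan nevertheless allows for invisible disease, since it samples normal cervices at both visits.

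**The large false-positive rates are conditional.** A reader might take 10% or 69% as the trial's error rate. The documents give no miss rate and do not say how the historical cohort was biopsied. If it shared the error, most of the inflation disappears. This stands in full.

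**The baseline site may not be where disease persists.** Treatment can use overlapping applications (5.5), and the endpoint is absence of dysplasia anywhere. This stands as a reason not to limit sampling to one site; it is no reason to leave the known site out.

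**Operational documents may cover it.** Section 8.7 plans SOPs and a study manual. They may, but a rule that determines the primary outcome belongs in the protocol.

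**Conclusion.** The gap holds. For women with baseline CIN2/3 and a normal colposcopy at 12 months, the plan requires a biopsy (3.1, 5.8), names no site, and does not require the baseline site to be kept. Under 7.1, residual disease that is both invisible and missed counts as cure, so this error can only bias the CIN2/3 cure rate upward.

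Its size cannot be derived from the documents. For an assumed 2.5% to 30% of uncured women misclassified, at n=140 and a true cure rate of 67.2%, the false non-inferiority rate rises from 1.8% to between 2.9% and 69% if the historical rate is free of this error. If the historical cohort had the same miss rate and the margin is taken on true rates, it rises only to between 2.1% and 8.9%. The net bias against the cryotherapy rate is therefore unknown.

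The documents do not establish that these women will be sampled at 6 or 12 o'clock, or that the trial's error rate is any particular figure. Section 7.1 also conflicts with 3.1 and 5.8 on who has colposcopy and biopsy at all, and that has to be settled for a site rule to work. The change is worth making before enrolment, because a baseline site that was not recorded cannot be reliably recovered later.

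**What to change.** 1. In section 5.4, record the clock position of each baseline biopsy and label specimens by site.
2. In sections 3.1 and 5.8, state that for women with baseline CIN2/3 and no visible lesion at 12 months, the biopsy already required includes the recorded baseline lesion site. Do not limit the number of specimens.
3. Reconcile section 7.1 with 3.1 and 5.8 on which women have colposcopy and biopsy at 12 months.

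The cost is one form field, which must be carried forward to the 12-month visit form, and a few sentences of protocol text. The site rule adds no visit and no new biopsy requirement beyond 3.1 and 5.8.

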5.9 Medical Record Data Collection

Individual participant data, including demographic and clinical information, will be collected from paper and electronic medical record at FACES and recorded into study-specific data collection forms. Participants will be enrolled in FACES for HIV-care and have regular laboratory monitoring of CD4+ counts and viral loads.

Predictor demographic variables will include participant age, gravidity, parity, history of cervical cancer screening, marital status, and the number of current and previous sexual partners. Clinical variables include current WHO status, CD4+ count levels, previous sexually transmitted infections, contraceptive use, and ongoing use of antiretroviral therapy.

6 Data Quality and Management

